3.2 Safety Endpoints

- Incidence of solicited AEs through Day 8 for PXVX0317 and placebo.
- Incidence of unsolicited AEs through Day 29 for PXVX0317 and placebo.
- Incidence of AESI and SAEs and MAAEs through Day 183 for PXVX0317 and placebo.

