The denominator for solicited AE tables comprises only those participants with at least one diary observation (i.e., any non-missing values but excluding "Not done/unknown"), at least one diary observation for a given symptom, or at least one diary observation for a given day, as applicable. *Note that an elevated in-clinic temperature assessment as part of 30-min post-vaccination vital signs does not count as a solicited AE, as vital signs data are summarized separately.*

AE, treatment-emergent. AE collection begins at Day 1 (baseline), the day of IP administration. AEs occurring after a participant has given informed consent, but before vaccination, are excluded from summaries. Only treatment-emergent AEs are summarized.

AEs, unsolicited, are defined as those AEs not listed in the e-diary or paper diary but collected in the EDC. Unsolicited AEs were to be collected though Day 29 unless they were SAEs, AESI, or MAAEs; unsolicited AEs starting on Day 30 or later that are not SAEs, AESI, or MAAEs are excluded from tabulations.

Age at screening visit is automatically calculated by EDC based on date of birth versus date of informed consent. Age at baseline (Day 1) is be summarized in all outputs.

Age group strata are defined as ages 12 to <18, 18 to <46, and 46 to <65 as randomized. Note that, if a participant is randomized into a stratum and their age is later corrected such that they should have been placed into a different age stratum, the participant is analyzed according to the corrected age stratum for immunogenicity analyses.

Analysis visits are defined in Section 5.5.

Analysis populations are defined in Section 5.3.

Baseline is defined in Section 5.6. Change from baseline is defined as (value at post-baseline assessment – value at baseline).

Baseline seropositive rate is defined as the percentage of participants with anti-CHIKV human SNA assay titer \geq LLOQ.

Body mass index at screening visit is automatically calculated by EDC as a participant's weight in kg divided by height in m^2 .

Anti-chikungunya virus (anti-CHIKV) human SNA assay NT₈₀ (80% neutralizing titer) is defined as the dilution factor that corresponds to an 80% reduction of luciferase activity compared to virus-only control. Anti-CHIKV SNA titer values below LLOQ are replaced by LLOQ/2 in the immunogenicity analyses including GMT and GMFI. For the 4-fold rise over Day 1 (baseline), values below the LLOQ are replaced with the LLOQ.

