9.2.2.1 Electronic Diary Compliance

Participant compliance with e-diary or paper diary solicited adverse event entry are not summarized.

9.2.3 Unsolicited Adverse Events from Day 1 through Day 29

All unsolicited AEs occurring during the specified collection period in the study are recorded, regardless of their assessment of relatedness by the investigator. Unsolicited AEs include also those solicited AEs ongoing after seven days post-injection (Day 8), AESI, and SAEs.

All reported unsolicited AEs are summarized by treatment group according to MedDRA SOC, PT and highest reported severity. When an unsolicited AE occurs more than once for a participant, the maximum severity and closest relationship to treatment is counted. The unsolicited AE analysis includes unsolicited AEs judged by the investigator as at least possibly related to IP.

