14.3.2.6.1	Number of Days with Symptoms for Participants who Reported Solicited Adverse Events – Safety Population, All Ages Pooled			
14.3.2.6.2	Number of Days with Symptoms for Participants who Reported Treatment-related Solicited Adverse Events – Safety Population, All Ages Pooled			
14.3.2.7	Percentage of Participants with Solicited Adverse Events by Day on Study – Safety Population, All Ages Pooled			
14.3.3.1	Solicited and Unsolicited Adverse Events by System Organ Class, Preferred Term and Highest Reported Severity – Safety Population, All Ages Pooled and by Age Group			
14.3.3.2	Solicited and Unsolicited Adverse Events by Highest Reported Severity – Safety Population by Sex Subgroups			
14.3.3.3	Solicited and Unsolicited Adverse Events by Highest Reported Severity – Safety Population by Race Subgroups			

PXVX0317 Vaccine EBSI-CV-317-004 SAP

Table	Title			
14.3.3.4	Solicited and Unsolicited Adverse Events by Highest Reported Severity – Safety Population by Ethnicity Subgroups			
14.3.3.5	Solicited and Unsolicited Adverse Events Excluding Serious Adverse Events by System Organ Class, Preferred Term and Highest Reported Severity – Safety Population, All Ages Pooled			
14.3.4.1	Listing of Serious Adverse Events - Safety Population, All Ages Pooled			
14.3.4.2	Listing of Adverse Events Leading to Study Discontinuation – Safety Population, All Ages Pooled			
14.3.4.3	Listing of Adverse Events Leading to Death - Safety Population, All Ages Pooled			
14.3.5.1	Unsolicited Adverse Events in Descending Frequency by Preferred Term – Safety Population, All Ages Pooled			
14.3.5.2	Unsolicited Adverse Events by System Organ Class, Preferred Term and Highest Reported Severity – Safety Population, All Ages Pooled and by Age Group			
14.3.5.3	Unsolicited Adverse Events of Severe (Grade 3) or Higher Severity in Descending Frequency by Preferred Term – Safety Population, All Ages Pooled			
14.3.5.4	Unsolicited Adverse Events of Severe (Grade 3) or Higher Severity by System Organ Class, Preferred Term and Highest Reported Severity – Safety Population, All Ages Pooled			
14.3.5.5	Treatment-related Unsolicited Adverse Events in Descending Frequency by Preferred Term – Safety Population, All Ages Pooled			
14.3.5.6	Treatment-related Unsolicited Adverse Events by System Organ Class, Preferred Term and Highest Reported Severity – Safety Population, All Ages Pooled			

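### SAP 6.3 and the body of 9.2.3 do not hold the unsolicited AE tables to the Day 1–29 window of the primary safety endpoint

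*SAP*

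**What the plan says.** The endpoints have two windows. SAP 3.2 lists "Incidence of unsolicited AEs through Day 29 for PXVX0317 and placebo" and, separately, "Incidence of AESI and SAEs and MAAEs through Day 183 for PXVX0317 and placebo". Protocol 8.3.1 has the same two endpoints under its primary safety endpoints. SAP 9.2 repeats both windows and says that the categories are summarized separately.

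The derivation rule is in SAP 6.3. Unsolicited AEs "are defined as those AEs not listed in the e-diary or paper diary but collected in the EDC". The definition has no onset limit. The same entry then adds that "unsolicited AEs starting on Day 30 or later that are not SAEs, AESI, or MAAEs are excluded from tabulations".

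The analysis section is SAP 9.2.3, headed "Unsolicited Adverse Events from Day 1 through Day 29". Its text says "Unsolicited AEs include also those solicited AEs ongoing after seven days post-injection (Day 8), AESI, and SAEs" and "All reported unsolicited AEs are summarized by treatment group according to MedDRA SOC, PT and highest reported severity".

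In SAP Appendix I, the unsolicited AE tables are 14.3.5.1 to 14.3.5.6; for example, 14.3.5.2 is "Unsolicited Adverse Events by System Organ Class, Preferred Term and Highest Reported Severity – Safety Population, All Ages Pooled and by Age Group". None of these titles states a window. The high-level summary 14.3.2.1 also has rows for any unsolicited AE. SAEs, AESI and MAAEs have their own tables, 14.3.5.7 to 14.3.5.12.

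**The concern.** The endpoint counts events with onset by Day 29. The only sentence that tells a programmer what to do with later onsets removes some of them and leaves the rest: SAEs, AESI and MAAEs starting on Day 30 or later stay among the tabulated unsolicited AEs. No second rule takes those events out of the unsolicited tables.

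At stake is whether the reported percentage is the endpoint as named. A mixed table would count all AEs for 29 days, plus the serious, special-interest and medically attended ones for the remaining 154 days. If late events are mainly background illness equally common in both arms, they raise both percentages and pull the comparison between arms toward no difference. Two programmers working from the same SAP could also produce different figures for a primary safety endpoint.

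**Working it through.** The plan states no figure that depends on this point, so the main check is of the text. A short illustration of size follows.

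**Text check: an MAAE with onset on Day 120**

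1. It is recorded in the EDC and is not a diary item, so under SAP 6.3 it is an unsolicited AE.
2. It starts on Day 30 or later, but it is an MAAE, so the SAP 6.3 exclusion does not remove it.
3. SAP 9.2.3 summarizes all reported unsolicited AEs by SOC, PT and severity. That sentence contains no onset condition, so the event is eligible for the unsolicited tables.
4. The event also belongs in the MAAE table 14.3.5.11, under the Day 183 endpoint.
5. The endpoint in SAP 3.2 and Protocol 8.3.1 stops at Day 29, so the event should not count there.

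Steps 3 and 5 conflict. A late SAE or AESI takes the same path, and 9.2.3 names both as unsolicited AEs. It does not name MAAEs; those enter through the SAP 6.3 definition and exception.

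The text that points the other way is the 9.2.3 heading, the windows in SAP 9.2, and the opening of 9.2.3, which refers to the specified collection period. SAP 2.2 gives that period as 28 days after vaccination for unsolicited AEs, but as Day 1 to Day 183 for SAEs, AESI and MAAEs. The reference to a collection period therefore does not settle which window applies to an event that is both unsolicited and, say, medically attended.

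**Length of the two periods**

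- Days 30 to 183: 183 − 30 + 1 = 154 days.
- Relative to the endpoint window: 154 / 29 = 5.3.
- Share of follow-up: 154 / 183 = 84%.

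**Illustration of size (assumed rates)**

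Let p be the true incidence through Day 29 and q the proportion of each arm with an SAE, AESI or MAAE starting on Day 30 to 183. The documents give neither. Assume that q is equal in the two arms and independent of p. The mixed incidence is then 1 − (1 − p)(1 − q), which exceeds p by (1 − p)q. The risk difference is multiplied by (1 − q).

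With p = 18% for vaccine and 14% for placebo (difference 4.0 points, ratio 18/14 = 1.29):

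| q | Vaccine | Placebo | Difference | Ratio |
|---|---|---|---|---|
| 5% | 1 − 0.82 × 0.95 = 22.1% | 1 − 0.86 × 0.95 = 18.3% | 3.8 points | 1.21 |
| 10% | 1 − 0.82 × 0.90 = 26.2% | 1 − 0.86 × 0.90 = 22.6% | 3.6 points | 1.16 |
| 15% | 1 − 0.82 × 0.85 = 30.3% | 1 − 0.86 × 0.85 = 26.9% | 3.4 points | 1.13 |

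Over a wider grid, p from 10% to 30% and q from 2% to 15%, the reported percentage rises by between 0.70 × 2% = 1.4 points and 0.90 × 15% = 13.5 points. The level is affected more than the absolute difference.

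**The case against.** A reader might infer that no planned table delivers the Day 29 endpoint. The documents do not support that, for these reasons:

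- The SAP 6.3 rule speaks of tabulations in general and names no table. It does not direct late events into the unsolicited tables.
- Its exception is needed in any case. Without it, late SAEs, AESI and MAAEs would drop out of the Day 183 tables. Protocol 8.7.2.2 lists the SAE, AESI and MAAE summaries under the unsolicited AE heading, so the exception may be meant only for those.
- SAP 9.2 and the 9.2.3 heading do state the Day 29 window. A programmer who followed them would produce the endpoint. The sentence adding AESI and SAEs can be read as limited by that heading.
- Titles without a window prove little. The SAE and MAAE table titles do not state Day 183 either.
- SAP 1 says that some derivation details are in programmer's notes in the TFL shells, which are not available here.

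A reader might also infer that an early vaccine signal would be hidden. That is not established. Safety endpoints are reported for information only, without formal testing (Protocol 8.6.2.5.2; SAP 6.4.2 and 6.9.2). The tables also show events by SOC and PT and show treatment-related events separately. The participant listings are ordered by AE start date, so a Day 29 cut could be recovered.

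These points narrow the concern but do not remove it. The exception explains why one filter cannot serve both sets of tables; it does not supply the second filter. A heading that disagrees with the derivation rule and with the text beneath it is an inconsistency. The shells cannot settle it, since SAP 1 calls them only a guide that may be updated. The window of a primary safety endpoint belongs in the SAP text.

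**Conclusion.** The point holds as a conflict within the SAP. The derivation rule in 6.3 and the body of 9.2.3 do not agree with the Day 1–29 window in Protocol 8.3.1, SAP 3.2, SAP 9.2 and the 9.2.3 heading. The only explicit onset rule keeps SAEs, AESI and MAAEs with onset from Day 30 among tabulated unsolicited AEs, and no written filter limits the unsolicited tables to onset by Day 29. A literal reading gives a mixed incidence that is not the stated endpoint. It is not shown that the tables will be produced that way.

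No size can be derived from the documents. The illustrated changes rest wholly on assumed rates, equal in the two arms and independent of early events. On those assumptions the absolute difference between arms changes little, while the percentages themselves can move substantially. The formal immunogenicity tests are unaffected. The reason to act is that a primary safety endpoint should have one unambiguous window, and this one can be fixed very cheaply.

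**What to change.** - In SAP 6.3 and 9.2.3, state that tables 14.3.5.1 to 14.3.5.6 and the unsolicited AE rows of 14.3.2.1 include only events with onset on Day 1 through Day 29, whether or not they are SAEs, AESI or MAAEs.
- State that SAEs, AESI and MAAEs with later onset are reported in tables 14.3.5.7 to 14.3.5.12. The existing exception in 6.3 can stay for that purpose.
- State the onset window used in the combined solicited and unsolicited tables 14.3.3.x.

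The cost is a few sentences in the SAP and one onset-date filter in programming. No new data are needed, and no event is lost from reporting because late SAEs, AESI and MAAEs remain in their own tables.

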8.7.2 Adverse Events

Adverse events will be coded to SOC and PT using the MedDRA dictionary. Solicited AEs, unsolicited AEs, AESI, MAAEs, and SAEs will be summarized separately by treatment group and maximum severity for the safety population for all age strata combined as well as for separate age groups.

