2.3.2 Randomization Errors

A *misrandomization* is defined as a participant receiving a study treatment other than the one assigned by randomization.

A *stratification error* occurs when a participant is randomized based on incorrect stratification information at Day 1 (baseline) or if a participant is mistakenly put into a wrong block.

In either case, the participant uses up one position in the assigned block and randomization continues. Both misrandomization and stratification errors are reported as protocol deviations.

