5.2.1 Important Deviations

Important protocol deviations are defined by ICH E3 (ICH, 1996) as those "that might significantly affect the completeness, accuracy, and/or reliability of the study data or that might significantly affect a participant's rights, safety, or well-being". Examples of important protocol deviations include:

- Participants who were enrolled/randomized but did not meet study eligibility criteria.
- Participants randomized but not treated.
- Participants with misrandomization or stratification errors.
- Participants who received a prohibited prior or concomitant medication or vaccine.
- Participants who previously received an investigational CHIKV vaccine/product, including but not limited to prior vaccination in EBSI-CV-317-004.
- Other deviations from key study procedures such as accidental unblinding or participant noncompliance with assessment of primary outcome measures (e.g., missing serum samples, significantly out of window assessments).

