5.3 Analysis Populations

Analysis are based on the following study populations:

Randomized Population: All screened participants who provide informed consent (and assent for adolescent participants 12 to <18 years of age) and provide demographic and other screening measurements and are randomized (i.e., have a randomization number assigned within the EDC system). Most baseline summaries and the IP administration summary use the randomized population.

Exposed Population: All participants in the randomized population who receive IP.

Safety Population: All participants in the exposed population who provide safety assessment data. This generally includes any participant who was not lost to follow-up at Day 1 (baseline), as they are at risk for reporting an SAE. Participants are analyzed as treated (i.e., according to the treatment a participant received, rather than the treatment to which the participant was randomized). All safety analyses use the safety population.

Modified Intent-to-Treat (mITT) Population: All randomized participants who are vaccinated and have at least one post-injection anti-CHIKV human SNA assay result. Participants are counted in the group to which they were randomized. Primary and secondary

immunogenicity analyses are repeated for the mITT population as a measure of robustness of the results.

Immunogenicity Evaluable Population (IEP): The IEP includes all participants in the mITT population who:

- Provide evaluable serum sample results for the relevant post-vaccination time points, and within the required time frames:
 - Day 22: Day 19 through Day 27, inclusive.
- Have no measurable (*ELLOQ*) anti-CHIKV human SNA assay titer at Day 1 (baseline), i.e., seronegative at baseline. Note that participants with missing Day 1 (baseline) are excluded from IEP.
- Have no important protocol deviation deemed exclusionary or other reason to be excluded as defined prior to unblinding.

The IEP is the primary population for all immunogenicity analyses.

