9.2.1 Overall Summary of Solicited and Unsolicited Adverse Events

A high-level summary of solicited and unsolicited AEs combined reviews the frequency counts and percentages of participants by treatment group reporting AEs in each of the following categories:

- Any AE and any AE \geq Grade 3
- Any solicited AE and any solicited AE \geq Grade 3

- Any treatment-related solicited AE and any treatment-related solicited AE \geq Grade 3
- Any unsolicited AE and any unsolicited AE \geq Grade 3
- Any SAE
- Any treatment-related SAE
- Any AE leading to study discontinuation
- Any fatal AE
- Any AESI (see definition in Section 6.3)
- Any MAAE and any treatment-related MAAE

In addition, summaries of combined solicited and unsolicited AEs by SOC, PT and highest reported severity are provided for the following populations:

- Safety population, all age groups
- Safety population by age strata
- Safety population by sex
- Safety population by race group
- Safety population by ethnicity
- Safety population by product lot

9.2.2 Solicited Adverse Events from Day 1 until Day 8

Solicited AEs recorded daily in the e-diary or paper diary until Day 8 include local (i.e., pain, redness, and swelling) and systemic reactions (i.e., fever, chills, fatigue, headache, myalgia, arthralgia, and nausea). In addition, solicited AEs ongoing after seven days post-injection (Day 8) and those that are serious or MAAEs are also recorded as unsolicited AEs. Severity of solicited AEs is assessed by the investigator in the same manner as unsolicited AEs.

Frequencies and percentages of participants experiencing each solicited AE are presented by maximum severity and by treatment group. The following summaries of solicited AEs are produced:

- Solicited AEs by maximum event severity, for each event and for any event
- Solicited AEs of severe (Grade 3) or higher severity, for each event and for any event
- Treatment-related solicited AEs by maximum event severity, for each event and for any event
- Day of first onset of solicited AEs, for each event and any event
- Duration of solicited AEs, for each event and any event
- Solicited AEs by day post-injection for each event and for any event

Occurrence of at least one AE by category (local, systemic) for solicited AEs are also included.

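### SAP 6.3 applies a corrected age stratum to immunogenicity only; read as written, by-age safety and demography tables keep a stratum known to be wrong

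*SAP*

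**What the plan says.** The rule is in SAP 6.3 (Derived Variables). The default is "Age group strata are defined as ages 12 to <18, 18 to <46, and 46 to <65 as randomized". The next sentence covers a participant whose age is corrected after randomization so that another stratum applies: "the participant is analyzed according to the corrected age stratum for immunogenicity analyses". No other age-stratum rule appears in either document.

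The plan expects such cases. SAP 2.3.2 defines a stratification error and says "Both misrandomization and stratification errors are reported as protocol deviations". SAP 5.2.1 gives "Participants with misrandomization or stratification errors" as an example of an important deviation.

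Safety is to be reported by age. Protocol 8.7.2 calls for each class of adverse event to be summarized "for the safety population for all age strata combined as well as for separate age groups". SAP 6.8 repeats summaries for each age group. SAP 9.2.1 lists "Safety population by age strata" among the displays of combined adverse events. SAP 9.3.2 and 9.3.4 do the same for serious and medically attended events. In SAP Appendix I the by-age safety tables are 14.3.2.2.1, 14.3.3.1, 14.3.5.2, 14.3.5.7 and 14.3.5.11. The by-age demography tables are 14.1.4.1 to 14.1.4.4.

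**The concern.** A table headed by an age group claims that the people in it are that age. The SAP accepts this for titers and moves a participant once the true age is known. For adverse events it falls back on the stratum entered at randomization, even where that is recorded as an error. The same person can then count as an adolescent for immunogenicity and an adult for safety.

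Safety is a coprimary objective, and Protocol 1.4 justifies the inclusion of adolescents separately. The adolescent and older-adult groups have the smallest enrolment targets, so one misplaced person weighs most there. At stake are the descriptive adverse event rates for those groups, and an avoidable discrepancy that someone would have to explain in the study report.

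**Working it through.** **Step 1. Which stratum applies to which output.** The rule has a general default and one exception.

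| Output | Covered by the exception? | Stratum used after an age correction |
|---|---|---|
| By-age titer and seroresponse tables | Yes | Corrected |
| Lot-consistency set, 18 to <46 | Yes | Corrected |
| By-age safety tables | No | As randomized |
| By-age demography tables | Not stated | As randomized by default |

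The safety row is the firmest, because no reading makes an adverse event table an immunogenicity analysis. The demography row is less certain: SAP 8.2 sits inside the SAP's immunogenicity chapter, so a programmer might apply the exception there. The SAP does not settle it.

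**Step 2. Is there a reason to keep the randomized stratum for safety?** It could be defended if the stratum were a factor in a model. Here it is not. Under SAP 6.1.2 and 6.6 the ANOVA models contain treatment group or lot, plus site; the conditional ANCOVA adds baseline titer. Safety is descriptive. The randomized stratum therefore enters no model, and the SAP already sets it aside for the coprimary immunogenicity analyses.

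**Step 3. Size.** The plan states no figure on this point, so there is none to reproduce. The inputs are the planned minimum enrolment in each of the youngest and oldest groups (Protocol 3.1.2, SAP 2.2): 210 vaccine and 35 placebo. These match the 2:2:2:1 allocation of 245 participants: 245 × 6/7 = 210 and 245 × 1/7 = 35.

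Suppose one of the n people in a column does not belong there and has the event, while x of the other n − 1 have it. The tabulated rate minus the true rate is

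(x + 1)/n − x/(n − 1) = (n − 1 − x) / [n(n − 1)],

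which is largest at x = 0, where it equals 1/n.

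- Vaccine: 1/210 = 0.48 percentage points.
- Placebo: 1/35 = 2.86 percentage points.

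The number of corrections is not given. As an assumed range, 1 to 5 misplaced participants in one column have a combined weight of 0.5 to 2.4 points for vaccine (5/210) or 2.9 to 14.3 points for placebo (5/35). The upper placebo figure is a ceiling and not an expectation: under 6:1 allocation about six of every seven misplaced participants would be in the vaccine column. With no corrections the effect is nil. Larger strata reduce all these figures.

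**The case against.** The SAP never says outright that safety tables keep a wrong stratum; this follows from the default plus an exception that does not mention safety. SAP 1 places some derivation details in programmer's notes in the table shells, which are not part of these documents, so the actual programming may differ. That stands as a limit on certainty about what would be produced. It does not repair the SAP, because a programmer following the text alone would use the randomized stratum.

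It is also fair to say that affected participants remain traceable. Stratification errors are deviations, important deviations are listed by participant, and SAP 7.1 puts the stratum in the randomization listing. A determined reader could reassign them, but should not have to.

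A reader might infer more than the documents support:

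- **Birthdays between consent and dosing.** SAP 6.3 says the EDC calculates age at consent, which may suggest that people crossing a boundary before Day 1 are also misplaced. No text says the stratum follows age at consent. SAP 2.3.1 places randomization on Day 1, and SAP 2.3.2 defines the error by Day 1 information. A birthday is also not a corrected age.
- **Conflict with the as-treated rule.** The safety population rule in SAP 5.3 concerns the treatment received and says nothing about age.
- **Mismatched denominators.** Safety and immunogenicity denominators differ by design, since the immunogenicity evaluable population has its own entry conditions and may exclude someone with a stratification error.
- **A threat to the trial's conclusions.** SAP 6.4.2 reports all safety endpoints for information only, and the coprimary immunogenicity analyses already use the corrected stratum.

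**Conclusion.** The point holds in a narrow form. As written, SAP 6.3 leaves a participant with a corrected age in the wrong stratum in the by-age safety tables and, by default, in the by-age demography tables. The by-age immunogenicity tables use the right one. Nothing in the documents justifies the split.

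The consequence is small and confined to descriptive tables. It rests on two things: reading the SAP text without its table shells, and at least one age correction that crosses a stratum boundary. At the planned minimum group size, one such participant is worth up to about 0.5 points for vaccine or 2.9 points for placebo. All-ages safety and every formal test are unchanged. This is a free improvement and not a flaw in the design.

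**What to change.** In SAP 6.3, delete the closing words that restrict the corrected stratum to immunogenicity, and state that it is used for all by-age summaries: demography, immunogenicity and safety. Keep the randomized stratum in the randomization listing and continue to report stratification errors as deviations. Check that the notes in the table shells agree.

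Do not use this edit to redefine the stratum by age at Day 1. That is a separate question, and it could move participants into or out of the 18 to <46 set used for the coprimary lot-consistency test.

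The cost is one phrase and the reuse of a variable already derived for immunogenicity. It needs no new data and changes no model or hypothesis test. It is best made before unblinding.

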- For participants seronegative at baseline (anti-CHIKV SNA titer <LLOQ), a seroresponse is defined as an anti-CHIKV SNA titer at Day 22.
- For participants seropositive at baseline (anti-CHIKV SNA titer ≥LLOQ), a seroresponse is defined as ≥4-fold rise from Day 1 (baseline) in anti-CHIKV SNA titer at Day 22.

Study Day 1 is defined as the day of IP administration on Day 1 (baseline). The day prior to Day 1 is Day -1. There is no Day 0. If the participant is not treated, then the Day 1 (baseline) is defined as the day of randomization.

Study day relative to Day 1 are calculated as:

- Study Day = (assessment date date of Day 1 + 1) if the assessment is on or after Day 1.
- **Study Day** = (assessment date date of Day 1) if the assessment is before Day 1.

For conversion of durations, 1 year = 365.25 days and 1 month = 365.25/12 = 30.4375 days.

Subgroups for sex (male and female), race (white and non-white) and ethnicity (Hispanic or Latino and Not Hispanic or Latino) are defined based on the corresponding demographic questions. Participants missing sex, race or ethnicity will be omitted from analyses by subgroup. Participants with "Not Reported" or Unknown" ethnicity are not included in ethnicity subgroups. Product lot subgroups are defined based on the lot variable in the randomization module dataset.

Summary statistics are described in Section 6.1.

Time duration (in days) between event A and event B is (date of event B – date of event A + 1). For conversion of durations, 1 year = 365.25 days and 1 month = 365.25/12 = 30.4375 days.

Treatment, actual, is defined as the treatment administered to the participant by the site (i.e., corresponding to the kit number used).

Treatment group is defined as PXVX0317 vaccine vs. placebo.

Treatment, randomized, is defined as the treatment assigned to the participant by the EDC (i.e., corresponding to the kit number assigned).

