6.8 Subgroup Analysis

Summaries pool all age groups and are repeated separately for each age group. Analyses of the primary immunogenicity and safety endpoints are also summarized by sex, race, and ethnicity group along with treatment group. AEs are reported by product lot subgroup.

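### By-lot adverse event summaries use an as-treated population but take lot from the randomization dataset, and the lot variable for the lot-consistency analysis is left unsettled

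*SAP*

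**What the plan says.** **Safety.** SAP 5.3 says of the safety population: "Participants are analyzed as treated (i.e., according to the treatment a participant received, rather than the treatment to which the participant was randomized". The same entry assigns all safety analyses to that population. SAP 6.8 adds "AEs are reported by product lot subgroup", and SAP 9.2.1 lists "Safety population by product lot" among the combined solicited and unsolicited AE summaries.

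**Source of lot.** SAP 6.3, at the end of the entry on subgroups, reads: "Product lot subgroups are defined based on the lot variable in the randomization module dataset". The same section has a received-treatment concept, "Treatment, actual, is defined as the treatment administered to the participant by the site", tied to the kit number used. But it defines treatment group only as vaccine against placebo, so lot is not part of it. The lot letters A, B and C are introduced as randomization codes.

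**Lot consistency.** The IEP is a subset of the mITT population, for which SAP 5.3 says "Participants are counted in the group to which they were randomized". The IEP also requires that participants "Have no important protocol deviation deemed exclusionary or other reason to be excluded as defined prior to unblinding". SAP 6.4.1 nevertheless defines each lot's geometric mean titer (GMT) in the third coprimary hypothesis by the lot that IEP participants receive. SAP 6.1.2 names vaccine lot as the ANOVA factor without saying where it comes from.

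**Wrong kits.** SAP 2.3.2 defines misrandomization as receipt of a treatment other than the one assigned. SAP 5.2.1 gives it as an example of an important deviation. SAP 7.1 plans a participant listing of the treatment actually received, including lot number.

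**The concern.** A by-lot safety table exists to show what happened to the people who received each lot. If the population is as treated but the lot label is as randomized, the two rules disagree for exactly the participants they are meant to handle. Someone assigned lot A and injected from a lot B kit has any event counted against lot A. Someone assigned placebo and given vaccine moves into the pooled vaccine column but has no vaccine lot in the randomization variable, so the lot columns need not add up to the pooled column.

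For lot consistency, a programmer could defend either variable from the text. This is a coprimary endpoint, required for FDA. Lot-to-lot swaps analyzed by assigned lot pull the lot means together, which in an equivalence test favours the conclusion sought. The choice should therefore be written down before unblinding.

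**Working it through.** **1. The by-lot AE summary.** No arithmetic is needed to find the conflict; the rules are set side by side:

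| Item | Rule | Place |
|---|---|---|
| Population | as treated | SAP 5.3 |
| Treatment group | vaccine or placebo only | SAP 6.3 |
| Lot | randomization module dataset | SAP 6.3 |
| Lot actually received | recorded and listed, not defined as an analysis variable | SAP 7.1 |

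With 900 participants planned per lot, one misplaced person is 1/900 = 0.11% of a lot column. That is negligible for common events, but a rare serious event would sit in the wrong column.

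**2. The plan's own power figure.** Inputs from SAP 4.2: SD 0.455 on the log10 scale, margin 0.176, 207 per lot, 2.5% per one-sided test, true difference 0. The stated power is 95%.

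- SE = 0.455 × √(2/207) = 0.0447
- Power = 2Φ(0.176/0.0447 − 1.96) − 1 = 2Φ(1.975) − 1 = 0.952
- The t-based version gives 0.951.

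The figure is reproduced, per pair of lots.

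**3. Effect of lot swaps if those participants stay in the analysis by assigned lot.** Suppose a fraction w of each of two lots is exchanged and the true log10 difference is d.

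- Apparent mean of A = (1 − w)μA + wμB; apparent mean of B = (1 − w)μB + wμA
- Apparent difference = (1 − 2w)d

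A reciprocal exchange shrinks the difference by 2w; an error in one direction only shrinks it by w.

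Take the true ratio at the 1.5 margin (d = 0.176) and 300 per lot, the SAP 4.2 figure for ages 18 to <46. SE = 0.455 × √(2/300) = 0.03715. The probability of declaring that pair equivalent is then Φ((0.176 − apparent difference)/SE − 1.96); the opposite bound contributes nothing visible.

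| w (assumed) | Apparent difference | Apparent ratio | False equivalence |
|---|---|---|---|
| 0 | 0.1760 | 1.50 | 0.025 |
| 1/300 (one per lot) | 0.1748 | 1.496 | 0.027 |
| 1% | 0.1725 | 1.488 | 0.031 |
| 2% | 0.1690 | 1.476 | 0.038 |
| 5% | 0.1584 | 1.44 | 0.069 |

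For w = 1%: (0.176 − 0.1725)/0.03715 = 0.095, and Φ(0.095 − 1.96) = 0.031. The values of w are assumptions; the documents give no wrong-kit rate. Attribution by lot received holds the figure at 0.025.

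**4. A placebo recipient retained in a vaccine lot.** Assume a lot GMT of 1712 (the phase 2 value 28 days after a single 40 µg dose, Protocol 1.3.2) and a lower limit of quantitation (LLOQ) of 15, so that a non-responder is scored 7.5. The documents do not state the LLOQ.

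- At 270 evaluable per lot (300 less 10%): log10(1712/7.5)/270 = 2.358/270 = 0.0087, a factor of 1.020, or about 2%.
- The 1050 is a minimum. If each outer stratum enrols only its 245, then 3150 − 490 = 2660 remain, 2660 × 2/7 = 760 per lot and 684 at 90% evaluable. Then 2.358/684 = 0.0034, or about 0.8%.

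**The case against.** The strongest reply is that the sentence in SAP 6.3 closes an entry on subgroups (sex, race, ethnicity, lot), and lot is treated as a subgroup only for AEs. A reader might infer that the same as-randomized lot variable drives the equivalence analysis. The documents do not support that: neither SAP 6.1.2 nor 6.4.1 ties the ANOVA factor to the randomization dataset, and 6.4.1 speaks of lot received. This part of the reply stands. What remains is a conflict between that wording and the as-randomized rule inherited from the mITT.

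It can also be said that wrong-kit participants are already handled, because misrandomization is an important deviation and the IEP can exclude it. That stands in part. Exclusion is a case-by-case judgement made before unblinding, and syringes carry a kit number in place of a lot number (Protocol 5.1.3), so a blinded assessor may see a kit mismatch without knowing whether the lot differed. No rule says that receipt of a wrong lot excludes, and the mITT repeat keeps such participants.

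A reader might also infer that as-treated safety tables in general are affected. They are not: SAP 5.4 and 6.7 pool lots outside lot consistency, and Appendix I lists no by-lot AE table at all.

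Finally, the documents do not say whether the randomization module's lot variable is updated to the kit used. If it is, the AE conflict disappears in practice, but the SAP would still need to say so.

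**Conclusion.** The inconsistency is real for the by-lot AE summaries: the population is as treated, lot comes from the randomization dataset, and no actual-lot variable is defined. This assumes that the dataset holds the assigned lot.

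For lot consistency the finding is narrower: two rules in the SAP point to different lots, and the safeguard that would make the choice immaterial is discretionary. It would be too strong to say that misattribution always favours equivalence. Swaps between vaccine lots do shrink a true difference. A retained placebo recipient instead lowers one lot's GMT, and between truly equal lots that pushes the means apart.

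The size is small. One retained swap per lot moves false equivalence at the margin from 0.025 to about 0.027, and a 1% exchange moves it to about 0.031, per pair, at 300 per lot with SD 0.455. Both figures require that the participants are not excluded. Larger lots would make a single error matter less. This is a minor point, worth settling because it is easy to settle.

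**What to change.** - In SAP 6.3, define actual lot as the lot of the kit number used, and apply it to every by-lot AE summary.
- In SAP 6.1.2 and 6.4.1, state that the IEP lot-consistency ANOVA uses lot received and that the mITT repeat uses randomized lot.
- State whether receipt of a wrong-lot kit excludes a participant from the IEP.
- Add the by-lot AE table to Appendix I, or remove the request from SAP 6.8 and 9.2.1; align SAP 5.4 accordingly.

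The essential change is one sentence in SAP 6.3, with short clarifications elsewhere. No new data are needed, since actual lot is already to be listed by participant under SAP 7.1. The wording should be settled before unblinding.
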